During CGM wear, a sterile disposable glucose sensor is applied on the abdomen and held in place with an adhesive. The wire-like sensor is not significantly thicker than the needles used in syringes for insulin injection. The needle insertion depth ranges from 0.35 – 0.55 inches.

Once in place, the sensor pod consists of a glucose oxidase-based electrochemical sensor placed subcutaneously to measure interstitial glucose concentrations over a 40-400 mg/dL range. The transmitter attached to the sensor pod will wirelessly send the sensor's glucose measurements via Bluetooth to a smartphone for display of trends and continuous glucose readings every 5 minutes. Readings will also be stored in the cloud. In using cloud storage, the smartphone also permits protected sharing of data with coaches and other authorized study staff. The smartphone also provides a more user-friendly interface, including larger text. Alerts, alarms, and reminders will be set to minimize disruption for the patient while still supporting proper use of the device and allowing for patient customization.

Participants will need to calibrate their CGM systems using a commercially available blood-glucose meter per manufacturer instructions.

As part of the system's instructions for use, users are informed of the following:

- The system does not replace blood glucose measurements.
- Blood glucose values may differ from sensor glucose readings and the value from the blood glucose meter should be used for treatment decisions.
- Symptoms of high and low glucose should not be ignored. If sensor readings do not fit with symptoms, blood glucose should be measured with a blood glucose meter.

Upon completion of 10 weeks of CGM use, patients will be asked to return their CGM transmitters and unused sensors. Patients will be allowed to keep their smartphones and activity trackers as long as they continue to sync the tracker at least every three weeks through the end of the study.

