#### **Activity Tracker System**

To help patients observe how physical activity impacts glucose levels, patients will be provided with a Fitbit Charge 2 wrist-worn activity tracker. This activity tracker will display in real-time the cumulative number of steps taken by the patient each day. The patient will also be able to view his/her step history via an app on the smartphone. The Fitbit activity tracker system consists of an activity tracker, a compatible charging cable, and an associated smartphone app that syncs step data to the Cloud.

Patients will be offered the option to use the activity tracker once they understand and are comfortable using their CGM systems and are ready to learn about physical activity.

Per protocol, patients will be asked to use their activity trackers through February 28, 2018. If patients sync their tracker data at least once every three weeks from the time they start using the activity tracker through February 28, 2018, then patients will be allowed to keep their activity tracker and smartphone. The data plan used during the study to sync data from devices will be terminated at the end of the study or when patients withdraw, which ever comes first.

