## 8. Treatment of Subjects

This program will provide dedicated resources to assure informed consent.

Patients will be instructed to continue to follow the advice of their physicians, including taking prescribed medications.

Patients will sign and date an IRB-approved consent form that indicates that if they are injured from applying or wearing the CGM system or activity tracker in the course of the program that they will receive treatment and that their insurance may be billed. Copays and costs related to injuries from applying or wearing the CGM devices and activity tracker which are not paid for by patient's insurance will be covered by Savvysherpa (Sponsor). Charges for medical care will be based on insurance contracted rates and not mastercharge sheet prices.

Patients with medical concerns related to the study devices will be instructed to contact the study doctor and/or his staff for evaluation. Patients with any other health will be encouraged to see their providers, or if needed, seek emergency assistance as part of their normal standard of care.

Patients and study staff will be provided with the device manufacturers' technical assistance telephone numbers to report any device-related problems or concerns.

Patients will be provided with a program phone number to call and report other problems or concerns.

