## 12. Risks

This is a minimal risk study. Program participants are being asked to wear a Fitbit activity tracker and a Dexcom CGM system.

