### Risks of the Activity Tracker Device

The Fitbit has a wrist band. Skin irritation from these devices is a remote possibility (there are very few reports in the online literature regarding this occurrence with similar devices). Study participants who experience skin irritation will be instructed to remove the activity tracker during sleep, and/or to alternate wearing it on the opposite wrist. There is also a slight risk that the privacy of the activity tracker data could be exposed if an unauthorized source hacks into the activity tracker's data system. Due to security and authorization that Savvysherpa has in place this risk is minimal.

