## 22. Appendix B

### Adverse Events Severity and Relatedness Questions

May 2017

When patients share a complaint, program coaches will identify the complaint in the Anticipated Complaints Guidebook. Based on the complaint type, coaches will then ask questions to determine:

1. Severity of the complaint (e.g., Mild, Moderate, or Severe), and
2. Relatedness of the complaint to the use of program devices (e.g., Not Related, Probably Not Related, Possibly Related, and Probably Related)

Coaches will document answers in the templates provided, including the Adverse Event document.

If the complaint falls in any of the severity categories highlighted in red, the coach will make a “warm transfer” to the study doctor and/or his staff so that the patient can be scheduled for an ancillary appointment.

If the complaint is an emergency, patients will be instructed to call 911.

If a patient has a complaint that is not listed in the Anticipated Complaints Guidebook, the coach can “warm transfer” the patient to the study clinic for guidance. The coach will document as much as possible in Adverse Event document. Follow up with the clinic will determine severity and relatedness.

Coaches will contact the PI when situations arise that are not covered in the Anticipated Complaints Guidebook.

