#### **Skin Redness or Rash – Relatedness Category**

1. Where is the location of the redness or rash?
  - If in the same location as the sensor on your skin, then Probably Related
  - If in a location where a sensor was within 2 days, then Possibly Related
  - If in a location where a sensor was 2+ days in the past, then Probably Not Related
  - If in a location where a sensor was never placed, then Not Related

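### The Appendix B coach scripts for rash and itch can rate irritation under the wrist activity tracker only as Not Related, because every answer asks about a CGM sensor

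*Protocol*

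**What the plan says.** The introduction to Appendix B tells coaches to establish, for each complaint, its severity and the "Relatedness of the complaint to the use of program devices", and gives four ratings from Not Related to Probably Related.

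The devices concerned are more than the CGM. The tracker has its own entry under Program devices in Section 6, where "patients will be provided with a Fitbit Charge 2 wrist-worn activity tracker". Section 12 opens by stating that "Program participants are being asked to wear a Fitbit activity tracker and a Dexcom CGM system". In the same section, under the activity tracker's risks, the protocol notes that the tracker has a wrist band and says "Skin irritation from these devices is a remote possibility".

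The sensor sits elsewhere on the body. Section 6, Dexcom CGM System, says that during wear "a sterile disposable glucose sensor is applied on the abdomen and held in place with an adhesive".

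In Appendix B, the relatedness parts of Skin Redness or Rash and of Skin Itchiness ask one question, the location of the complaint, and offer the same four answers. Each answer is defined by a sensor at that location: one there now, one there within two days, one there longer ago, or none ever. The fourth is "If in a location where a sensor was never placed, then Not Related".

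**The concern.** The stated scope of the rating and the answers that deliver it do not match. The scope is any program device, but the answers test for one device only. A coach who follows the script faithfully must give a tracker-site complaint the rating that denies any link to the program, although the protocol itself anticipates that kind of complaint.

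At stake is the safety description of a study device. The error runs in one direction, since these scripts can never give a tracker skin event a rating that points towards the tracker. Tracker wear also outlasts CGM wear: CGM use is 10 weeks, while participants are encouraged to wear the tracker through 28 February 2018 (Section 6, Program Length and Activity Tracker System). The script is thus blind to the only worn device that remains in the later part of the study.

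**Working it through.** There is no figure in the plan to reproduce. The check traces the decision rule for a complaint on the wrist under the band.

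**Inputs**
- Scope of the rating: program devices (Appendix B, introduction).
- Tracker site: wrist (Section 6, Activity Tracker System).
- Sensor site: abdomen (Section 6, Dexcom CGM System).
- Answers: the four sensor-location options (Appendix B, relatedness parts of redness/rash and of itchiness).

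**Do these scripts receive a wrist complaint?** Yes, on their wording. Most of the other scripts in Appendix B are titled as insertion-site problems (pain, swelling, bruising, bleeding, infection). These two are titled by skin symptom only, and their fourth answer expressly provides for sites away from any sensor.

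**Trace for redness, rash or itch under the band**

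| Condition in the answer | Rating | Reachable at the wrist? |
|---|---|---|
| Sensor is at that site now | Probably Related | No, sensor is on the abdomen |
| Sensor was there within two days | Possibly Related | No |
| Sensor was there more than two days ago | Probably Not Related | No |
| No sensor was ever there | Not Related | Yes, the only one |

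One of the four ratings can be reached, and it is the one that excludes a link.

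**After CGM ends.** Once the last sensor has been off for more than two days, the first two answers are closed for every body site. The highest rating that either script can then give anywhere is Probably Not Related, while the tracker may still be worn.

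**Do other parts of the protocol supply the missing criterion?**
- Section 6, Integration with patient care: the coordinator assesses severity and relatedness, but the text concerns health problems linked to the CGM devices.
- Section 8: patients with medical concerns about the study devices go to the study doctor or staff. This covers the tracker but gives no relatedness rule.
- Section 9: coaches connect patients who report adverse events with the coordinator for assessment and documentation. The device-related events it lists are sensor and adhesive events.
- Appendix B, introduction: the clinic decides relatedness for complaints not listed in the Anticipated Complaints Guidebook. Rash and itch have their own scripts. For complaints with a script, transfer to the clinic depends on severity and not on suspected cause.

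None of these gives a tracker criterion, and none says that the coach's documented rating is superseded.

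**The case against.** The strongest reply is that the coach's script is not shown to be the last word. The coordinator is trained to assess and document adverse events, participants can report directly to the coordinator or study doctor, and nothing binds those assessors to the coach's answer. The Anticipated Complaints Guidebook and the Appendix D guidance for coaches cited in Section 9 are not in the text available, so a separate tracker entry may exist. The script also asks for the location, so a recorded wrist site would let a later reader recognise a tracker event. Finally, redness or itch scored 1 to 5 is generally not recorded as an adverse event at all (the redness script makes an exception when itch or pain is moderate), and Section 12 regards band irritation as remote.

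All of this stands as a limit on the size of the point. It rules out two stronger readings that a reader might infer. The first is that every tracker skin event will end up recorded as unrelated, so that the study's count of related ones must be zero. The independent routes and the unseen material do not allow that. The second is that participants would lose the cover in Section 8 for "Copays and costs related to injuries from applying or wearing the CGM devices and activity tracker which are not paid for by patient's insurance". That section does not make payment depend on the coach's rating, so no loss of cover follows.

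The reply does not remove the defect in the scripts. A possible second assessor working without a stated criterion, and without a stated rule on whose rating prevails, does not correct a first rating fixed at Not Related.

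**Conclusion.** The point holds for the coach scripts as shown. Redness, rash or itch under the tracker band can be rated only Not Related, which contradicts the scope that Appendix B sets and sits badly with the risk that Section 12 names. Coach-recorded relatedness for tracker skin events is biased towards unrelated. Whether the final safety record carries the same bias depends on the coordinator, study doctor or clinic, and the protocol leaves that open.

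The size cannot be given as a number of events, because the protocol states no rate for tracker irritation. The planned enrolment of 100 is a ceiling on exposure, since tracker use is offered as an option once patients are comfortable with the CGM. The study tests no hypothesis and has no sample size calculation, so only the safety classification is affected.

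The conclusion assumes that the sensor is worn on the abdomen as described, that coaches apply the scripts as written, and that no separate tracker script exists in the material not shown. It is a modest defect, but a real one in an instrument that staff will use, and worth correcting because the correction is so cheap.

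**What to change.** Either of two changes would do.

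1. In the relatedness parts of the redness/rash and itchiness scripts, add an answer for a site under or next to the tracker band that rates relatedness to the tracker. Restrict Not Related to sites where no program device was worn. Add a field to the adverse event template for the device to which the rating refers.
2. Or state that these scripts rate relatedness to the CGM only, and send tracker-site skin complaints to the coordinator for rating.

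Under either option, state whether the coordinator's or study doctor's rating replaces the coach's in the safety record.

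The first option costs one added answer and one reworded answer in each of two scripts, plus one template field. The second costs a sentence of scope and a routing instruction. Neither adds a patient procedure.

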#### **Skin Itchiness – Severity Category**

1. On a scale of 1 to 10, where 1 is very little, and 10 is severe, how would you rate your skin itchiness?
  - If 1-5, do not record as AE
  - If 6-7, Mild AE
  - If 8-9, Moderate AE
  - If 10, Severe AE**

#### **Skin Itchiness – Relatedness Category**

1. Where is the location of the itchiness?
  - If in the same location as the sensor on your skin, then Probably Related
  - If in a location where a sensor was within 2 days, then Possibly Related
  - If in a location where a sensor was 2+ days in the past, then Probably Not Related
  - If in a location where a sensor was never placed, then Not Related

#### **Insertion Site Pain or Discomfort – Severity Category**

1. On a scale of 1 to 10, where 1 is very little, and 10 is severe, how much does your pain or discomfort affect your ability to do your daily activities?
  - If 1-2, do not record as AE
  - If 3-5, Mild AE
  - If 6-8, Moderate AE**
  - If 9-10, Severe AE**

#### **Insertion Site Pain or Discomfort – Relatedness Category**

1. Where is the location of the pain or discomfort?
  - If in the same location as the sensor on your skin, then Probably Related
  - If in a location where a sensor was within 2 days, then Possibly Related
  - If in a location where a sensor was 2+ days in the past, then Probably Not Related
  - If in a location where a sensor was never placed, then Not Related

### Insertion Site Swelling – Severity Category

1. On a scale of 1 to 10, where 1 is very little, and 10 is severe, how would you rate the amount of swelling?
  - If 1-5, do not record as AE
  - If 6-7, Mild AE
  - If 8-9, Moderate AE
  - If 10, Severe AE

### Insertion Site Swelling – Relatedness Category

1. Where is the location of the swelling?
  - If in the same location as the sensor on your skin, then Probably Related
  - If in a location where a sensor was within 2 days, then Possibly Related
  - If in a location where a sensor was 2+ days in the past, then Probably Not Related
  - If in a location where a sensor was never placed, then Not Related

### Insertion Site Bruising – Severity Category

1. On a scale of 1 to 10, where 1 is very little, and 10 is severe, how much bruising do you have?
  - If 1-5, do not record as AE, **unless the bruise is getting bigger, see question 2**
  - If 6-7, Mild AE
  - If 8-9, Moderate AE
  - If 10, Severe AE
2. Is the bruise or bump getting bigger?
  - If no, stop
  - If yes, **Moderate AE**
  - If yes and bruise is significantly getting bigger, **Severe AE**

### Insertion Site Bruising – Relatedness Category

1. Where is the location of the pain or discomfort?
  - If in the same location as the sensor on your skin, then Probably Related
  - If in a location where a sensor was within 2 days, then Possibly Related
  - If in a location where a sensor was 2+ days in the past, then Probably Not Related
  - If in a location where a sensor was never placed, then Not Related

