- There are no expected electrical safety risks as the device has passed the electrical safety tests as per EN45502-1 and EN60601;

- If the subject feels any discomfort during the course of the study, he/she will be able to remove the device immediately (the device is not permanent);
- The device is being used to complement, not replace, self-monitoring of blood glucose meter information, and readings are not intended to be used alone to make diabetes self-management decisions. As with the currently approved device and per intended use of similar technologies, subjects in the study will be instructed not to use the device for diabetes therapy or management;
- Subjects will be instructed to monitor their blood glucose levels as per their usual practice.

Adverse events (AE) associated with the use of the device include pruritus (severe itchiness present 48 hours after removal), erythema (reddening of the skin present 48 hours after removal), and inflammation (swelling and pain, defined as 8 or greater on a 10 point scale 48 hours after removal) where the adhesive touches the skin; local infection at insertion site; and shooting pain located at the site of the sensor (defined as 8 or greater on a 10 point scale). Rarely, the sensor wire will fracture when the sensor is being inserted, worn, or removed. If a sensor breaks and no portion of it is visible above the skin, the participant will be instructed to not remove it and seek medical care from the study doctor and/or his staff.

No serious adverse events (SAE) are expected as a result of participation in this minimal risk study. However, AE and SAE will be monitored in the following ways:

- Participants in the study will be instructed to call the study doctor's clinical research coordinator to report all AE and SAE related to the use of the study devices. The study doctor and/or his staff will assess the severity of any health problems associated with the device, and if needed, see the patient at the study clinic to assure appropriate care.
- Study coaches will listen for any reports of AE or SAE in the course of their communications with participants, and will connect reporting patients with the study doctor's clinical research coordinator so events can be assessed and documented and patients can receive care, if needed.

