#### Skin Redness or Rash – Severity Category

1. On a scale of 1 to 10, where 1 is very little, and 10 is severe, how would you rate the redness of your skin or rash?
  - If 1-5, do not record as AE, **unless itchiness and/or pain are moderate**
  - If 6-7, Mild AE
  - If 8-9, Moderate AE**
  - If 10, Severe AE**
2. Are you experiencing **pain or itchiness** where your skin is red or where you have a rash?
  - If no, stop.
  - If yes, on a scale of 1 to 10 where 1 is very little, and 10 is severe, how would you rate the **itchiness**?
    - If 1-5, do not record as AE
    - If 6-7, Mild AE
    - If 8-9, Moderate AE**
    - If 10, Severe AE**

- If yes, on a scale of 1 to 10 where 1 is very little, and 10 is severe, how would you rate the **pain**?
  - If 1-2, do not record as AE
  - If 3-5, Mild AE
  - If 6-8, Moderate AE**
  - If 9-10, Severe AE**

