### **Insertion Site Bleeding – Relatedness Category**

1. Where is the location of the bleeding?
  - If in the same location as the sensor, then Probably Related
  - If in a location where a sensor was within 2 days, then Possibly Related
  - If in a location where a sensor was 2+ days in the past, then Probably Not Related
  - If in a location where a sensor was never placed, then Not Related

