### **Detached/Broken Sensor Wire – Severity Category**

1. Do you see the sensor wire sticking out of your skin?
  - If no, then stop
  - If yes, then ask: On a scale of 1 to 10, where 1 is very little, and 10 is severe, how would you rate your pain or discomfort
    - If 1 – 7, **then Mild AE**
    - If 8 – 9, **then Moderate AE**
    - If 10, **then Severe AE**

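### Appendix B's bruising relatedness script asks where the pain is instead of where the bruise is, and sensor-site pain is scored on scales and cut-offs that do not match Section 9

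*Protocol*

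**What the plan says.** Appendix B of the protocol has coaches grade each complaint for severity and for relatedness to the program devices, and document the answers in templates.

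For bruising, the severity script asks about the bruise itself ("how much bruising do you have"), and a second item asks whether it is growing. The relatedness script that follows asks "Where is the location of the pain or discomfort". Its four answers depend on whether that location is the current sensor site, a site used within two days, an older site, or one never used. The neighbouring scripts name their own complaint: "Where is the location of the swelling" for swelling, "Where is the location of the bleeding" for bleeding.

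For insertion-site pain, the severity script asks "how much does your pain or discomfort affect your ability to do your daily activities". Scores of 1-2 are not recorded; 3-5 is Mild, 6-8 Moderate and 9-10 Severe. The redness/rash script asks "how would you rate the pain" with the same four bands. The broken-wire script asks "how would you rate your pain or discomfort", with 1-7 Mild, 8-9 Moderate and 10 Severe. Section 9 lists among the device adverse events "shooting pain located at the site of the sensor (defined as 8 or greater on a 10 point scale").

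**The concern.** In the bruising script, the answer that fixes relatedness describes a different symptom. A patient with a bruise and no pain cannot answer, and a patient whose pain is somewhere else answers about the wrong place. Either way the coach's relatedness label for that bruise may be blank or wrong.

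For pain, the protocol uses more than one measure and more than one threshold for what looks like the same event. Whether a report becomes an adverse event can then depend on which part of the protocol is applied. The device is investigational, and Section 9 has adverse events reported to the IRB, the manufacturer and the FDA, so these definitions should agree.

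**Working it through.** No arithmetic from the protocol is at issue; the check sets the scripts side by side.

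**Step 1. Does each relatedness question match its heading?**

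| Script | Asks for the location of |
|---|---|
| Redness or rash | redness or rash |
| Itchiness | itchiness |
| Pain or discomfort | pain or discomfort |
| Swelling | swelling |
| Bruising | **pain or discomfort** |
| Bleeding | bleeding |
| Infection | infection |
| Broken sensor wire | wire |

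Seven of eight match. The exception is identical to the pain script's question, which points to a copying slip rather than a choice.

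**Step 2. What follows if the bruising script is used as written?** Take a bruise at the current sensor site, scored 6, which the severity script records as Mild.

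- No pain: none of the four answers applies.
- Pain at the bruise: Probably Related, the same answer the bruise location would give.
- Pain where a sensor was within two days: Possibly Related, although the bruise location gives Probably Related.
- Pain where no sensor was ever placed: Not Related, although the bruise location gives Probably Related.

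In all four cases the bruise is still recorded as Mild, because the severity script decides that.

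**Step 3. What does each pain rule measure, and where does recording start?**

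| Place | Scored | Recorded from |
|---|---|---|
| Insertion-site pain script | effect on daily activities | 3 |
| Redness/rash script, pain item | pain itself | 3 |
| Broken-wire script, wire visible | pain itself | 1 (no unrecorded band) |
| Section 9, shooting pain at sensor | 10-point scale, construct not stated | 8 |

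**Step 4. Cross the insertion-site script with Section 9.** Let *I* be pain intensity and *A* the activity score for sensor-site shooting pain. The script records when *A* ≥ 3. If Section 9's scale is intensity, its rule is *I* ≥ 8.

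- *I* ≥ 8 and *A* ≥ 3: counted by both.
- *I* ≥ 8 and *A* ≤ 2: counted by Section 9, unrecorded by the script.
- *I* ≤ 7 and *A* ≥ 3: recorded by the script, not counted by Section 9.
- *I* ≤ 7 and *A* ≤ 2: counted by neither.

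Example: *I* = 8, *A* = 2. Section 9 calls this an adverse event and the rash script's bands would make it Moderate, but the insertion-site script does not record it. If there is no rash, sign of infection or visible broken wire, no other Appendix B script scores that pain.

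If Section 9's scale were instead effect on activities, every score of 8 or more would also be at least 3, so nothing would be lost. The remaining conflict would be scores of 3-7, which only the script records.

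**The case against.** The strongest reply is that Appendix B is a first screen. Under Section 6 the clinical research coordinator assesses severity and relatedness of device-associated problems. Section 9 tells participants to call the coordinator directly, has coaches listen for adverse events and connect those patients, and sends the manufacturer's reports to the coordinator as well. Coaches are trained, the heading above the bruising question names the topic, and they also use a complaints guidebook that is not in the document. All of this stands, and it limits the harm to what may happen. It does not make the question correct. A complaint that scores below the recording threshold also has no route to the coordinator within Appendix B, where transfer is tied to highlighted severity categories or to complaints outside the guidebook.

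A second reply is that grading pain by its effect on daily activities is a legitimate choice. That also stands: a reader might infer that the pain script asks the wrong question, but nothing in the document marks it as a mistake. Section 9 is also narrower (shooting pain) and does not say what its scale measures, and the rash and broken-wire items belong to other complaints. What survives is that the same bands are applied to two different constructs, and that the recording thresholds differ.

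A reader might also infer that device-related adverse events will be undercounted. The documents do not support that. The mismatch runs both ways, since the script records from 3 where Section 9 starts at 8, and no frequencies are given. Nor does the bruising error stop bruises from being recorded.

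**Conclusion.** The bruising relatedness question is a plain wording error in one of eight scripts. Used as written, it leaves painless bruises without a valid answer and may mislabel others; it affects only the coach-assigned relatedness category.

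The pain finding is an inconsistency in construct and cut-off. Sensor-site shooting pain of 8 or more with an activity score of 1-2 may go unrecorded by the coach although Section 9 defines it as an adverse event. This rests on reading Section 9's scale as intensity, which is natural but not stated. In the other direction, pain is recorded that Section 9 would not count. The net effect on the adverse event count cannot be determined from the protocol.

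Both are modest points of safety-data quality. Section 10 describes an exploratory evaluation with no hypothesis test or sample size calculation, and the effectiveness results do not depend on either script.

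**What to change.** In the bruising relatedness script, ask for the location of the bruising. This changes one noun and leaves the answer options as they are.

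For pain, reconcile Section 9 with the insertion-site pain, redness/rash and broken-wire scripts. State what Section 9's 10-point scale measures, and make the recording thresholds agree or explain why they differ. One workable route is to add a direct 1-10 pain rating to the insertion-site script beside the activity question, so that every event Section 9 defines as an adverse event is captured. Adding the question alone would not settle 3 against 8, so the cut-offs need an explicit decision by the sponsor and the medical co-investigators.

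The cost is a small edit to the coach scripts and templates, a clarifying sentence in Section 9, and a short coach briefing. If any complaints have already been collected, bruises with a missing or Not Related label should be checked against the recorded sensor site.
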